#### 3.4.2. Analysis of program impact pathways

The program impact pathway (PIP) was developed in collaboration with the A&T program team to map out the mechanisms through which the interventions were expected to achieve impact. The purpose of

the PIP analysis is to lay out the theoretical causal links between program activities, outcomes, and impacts. We will examine key indicators along the components of pathways (addressed in part by RQ2 and RQ3), to interpret and support the impact evaluation results. We will compare differences between program groups for indicators along the pathway matched to the relevant outcomes (dietary diversity, IFA consumption, and breastfeeding practices), using mixed-effects regression models, accounting for geographic clustering. Additional path analyses will be considered based on the results of the above analyses.

Table 7: Measures for program impact pathways

Outcome	Key Indicators	Data source
Service providers' capacity-building and service provision:		
Training and supervision (RQ3)	
 
- % NM received maternal nutrition training
 
- % ASBC received maternal nutrition training
 
- % NM/ASBC by training content
 
- % NM/ASBC received supervision
 
- % NM/ASBC by supervision content
 
	N-M survey ASBC survey
Service providers' knowledge (RQ3)	
 
- Knowledge scores for dietary diversity, adequate intake, IFA, and weight gain monitoring
 
- Knowledge scores for breastfeeding
 
	N-M survey ASBC survey
Service provision (RQ3)	
 
- % NM/ASBC provided maternal nutrition interventions
 
- % NM/ASBC by counseling messages provided (on dietary diversity, IFA, weight gain monitoring, and breastfeeding)
 
- % NM/ASBC used job aids for maternal nutrition counseling
 
- % ASBC provided home visits to PW/number of visits in last 30 days
 
- % ASBC conducted GASPA for PW/number of meetings in last 30 days
 
	N-M survey ASBC survey
Beneficiaries' exposure and behavioral determinants:		
ANC visits and contacts (RQ2)	
 
- # of ANC visits (at health facility)
 
- Total # of ANC contacts
 
- % RDW with at least 4 ANC visits
 
- % RDW with at least 8 ANC contacts
 
- % RDW received ANC visit in first trimester of pregnancy
 
- # of contacts outside of health facility (home visits and GASPA)
 
	PW survey RDW survey
Counseling on dietary diversity and adequate intake (RQ2)	
During ANC visits and other ANC contacts:
 
 
- % RDW received counseling on maternal nutrition
 
- % RDW received counseling on dietary diversity
 
- % RDW received counseling on consuming adequate quantity of food
 
	PW survey RDW survey
Counseling on IFA supplementation (RQ2)	
During ANC visits and other ANC contacts:
 
 
- % RDW received counseling on importance of IFA
 
- % RDW received counseling on how/reminders to take IFA
 
- % RDW received counseling on managing IFA side effects
 
	PW survey RDW survey
Weight gain monitoring and counseling (RQ2)	
During ANC visits and other ANC contacts:
 
 
- # times weighed
 
- % RDW weighted at least 4+ times/ at each ANC visit
 
- % RDW received counseling about weight gain during pregnancy
 
	PW survey RDW survey
Counseling on early breastfeeding practices (RQ2)	
During ANC visits and other ANC contacts:
 
 
- % RDW received counseling on breastfeeding practices
 
- % RDW received counseling on early initiation of breastfeeding
 
- % RDW received counseling on not feeding pre-lacteals
 
	PW survey RDW survey

	
 
- % RDW received counseling on exclusive breastfeeding
 
	
Beneficiaries' knowledge and perceptions	
 
- Knowledge scores for dietary diversity, adequate intake, IFA, and weight gain monitoring
 
- Knowledge scores for breastfeeding
 
- Beliefs, self-efficacy, and social norms score
 
	PW survey RDW survey

Table 8: Dummy table for program impact pathways analysis

Indicator	Baseline		Endline	
	A&T (N=)	Control	A&T	Control
	Mean (SD)			
(see indicators in Table 7)				
	Percent			

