2.2 Eligibility criteria

The study includes two main samples: pregnant women (PW) and recently delivered women (RDW), to assess diet during pregnancy (among PW) and intervention exposure throughout pregnancy (among RDW).

Inclusion criteria:

- 1) Women of reproductive age (15 to 49 years old)

- 2) Currently pregnant or having a living child under 6 months of age (recently delivered) at the time of the survey
- 3) Residency in the health center catchment area
- 4) Informed consent

Exclusion criteria:

- 1) Severe illness (e.g., any severe illness symptoms mentioned/identified by the woman, a relative or the enumerator) in woman and/or child requiring immediate hospital referral
- 2) Chronic or congenital illness (e.g., any health condition mentioned/identified by the woman, a relative or the enumerator) in women and/or child interfering with dietary intake

At the health center level, health staff particularly the nurse-midwife responsible for providing ANC, and community health workers are eligible to participate in one-to-one interviews after providing informed consent.

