## 2.2 Research question 2 (coverage and utilization)

For effects on coverage and utilization of interventions during ANC visits, outcome measures will be used from the RDW survey data. In the context of the overall evaluation, outcomes under this research question are considered as secondary outcomes.

Table 3: Outcome measures for RQ2

Outcome	Indicator	Data source
ANC visits and contacts	
 
- # of ANC visits (at health facility)
 
- Total # of ANC contacts
 
- % RDW with at least 4 ANC visits
 
- % RDW with at least 8 ANC contacts
 
- % RDW received ANC visit in first trimester of pregnancy
 
- # of contacts outside of health facility (home visits and GASPAs)
 
	RDW survey
Counseling on dietary diversity and adequate intake	
During ANC visits and other ANC contacts:
 
 
- % RDW received counseling on maternal nutrition
 
- % RDW received counseling on dietary diversity
 
- % RDW received counseling on consuming adequate quantity of food
 
	RDW survey
Counseling on IFA supplementation	
During ANC visits and other ANC contacts:
 
 
- % RDW received counseling on importance of IFA
 
- % RDW received counseling on how/reminders to take IFA
 
- % RDW received counseling on managing IFA side effects
 
	RDW survey
Weight gain monitoring and counseling	
During ANC visits and other ANC contacts:
 
 
- # times weighed
 
- % RDW weighted at least 4+ times/at each ANC visit
 
- % RDW received counseling about weight gain during pregnancy
 
	RDW survey
Counseling on early breastfeeding practices	
During ANC visits and other ANC contacts:
 
 
- % RDW received counseling on breastfeeding practices
 
- % RDW received counseling on early initiation of breastfeeding
 
- % RDW received counseling on not feeding pre-lacteals
 
- % RDW received counseling on exclusive breastfeeding
 
	RDW survey

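### SAP Table 7 adds still-pregnant women as a source for whole-pregnancy visit, contact and weighing counts, and the pathway models make no allowance for gestational age

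*SAP*

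**What the plan says.** SAP section 2.2 sets the source for the coverage and utilization outcomes: "For effects on coverage and utilization of interventions during ANC visits, outcome measures will be used from the RDW survey data". Every row of Table 3 lists the RDW survey alone. SAP section 1.3 explains why: RDW are the sample best placed to show exposure over the whole pregnancy.

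Table 7 in SAP section 3.4.2 repeats these indicators as pathway measures, but the source for all five blocks drawn from research question 2 becomes "PW survey RDW survey". Within those blocks:

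- The threshold rows are worded as percentages of RDW: "RDW with at least 4 ANC visits", "RDW with at least 8 ANC contacts" and "RDW weighted at least 4+ times/ at each ANC visit".
- Four counts name no population: facility visits, total contacts, contacts outside the facility, and the number of "times weighed".

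The protocol's inclusion criterion (section 2.2) is "Currently pregnant or having a living child under 6 months of age (recently delivered) at the time of the survey", with no lower or upper limit on gestation. The pathway comparison between arms is to be made "using mixed-effects regression models, accounting for geographic clustering", and no other covariate is named. By contrast, the adjusted impact models in SAP section 3.3 include gestational age for PW.

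**The concern.** A woman who is still pregnant has had only the visits, contacts and weighings that fell before her interview. If a whole-pregnancy total or threshold is computed in PW, it measures delivery and gestational age together.

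This matters because section 3.4.2 matches pathway indicators to outcomes, and dietary diversity, a primary outcome, is measured in PW. Exposure among PW is therefore the natural pathway evidence for that outcome. If the exposure measure is cut off at the interview and not adjusted, a real arm difference in contacts appears smaller than it is. Part of the remaining difference, or of the change between surveys, may reflect how far along the women were.

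The text also leaves the analyst without a clear instruction. Read by label, the thresholds belong to RDW; read by source column, they belong to both samples. Dummy Table 8 has one set of arm columns and does not separate the samples, so even pooling is not ruled out.

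**Working it through.** The plan gives no value for these indicators in PW, so there is no figure to reproduce. The check asks what PW would show if delivery were perfect.

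**Inputs from the documents.** The target is 8 contacts, at least 4 of them at the facility (SAP section I). PW are eligible at any gestation (Protocol 2.2). Planned samples per arm are 480 PW and 960 RDW (SAP Table 1).

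**Assumptions, none given in the documents and used for arithmetic only.** Gestational age at interview is uniform from g0 to 40 weeks, with g0 = 4, 8, 12 or 16. Contacts are evenly spaced from week f = 8 or 12 to week l = 36, 38 or 40, and every woman attends all of them. Facility visits are either four evenly spaced visits, alternate contacts, or all eight contacts.

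**Formulas.** With t_k the week of contact k:

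- share of PW who have reached k contacts = (40 − max(t_k, g0)) / (40 − g0)
- mean count to date = the sum of these shares over k

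**Extremes worked out.**

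- 8+ contacts, highest (g0 = 16, l = 36): (40 − 36)/(40 − 16) = 4/24 = 17%. Lowest (l = 40): 0%.
- Mean contacts, lowest (g0 = 4, contacts at weeks 12, 16, …, 40): (28 + 24 + 20 + 16 + 12 + 8 + 4 + 0)/36 = 112/36 = 3.1.
- Mean contacts, highest (g0 = 16, contacts at weeks 8, 12, …, 36): (24 + 24 + 24 + 20 + 16 + 12 + 8 + 4)/24 = 132/24 = 5.5.

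| Indicator in PW, perfect delivery | Range | Value at delivery |
|---|---|---|
| 8+ contacts | 0% to 17% | 100% |
| 4+ visits, four evenly spaced | 0% to 17% | 100% |
| 4+ visits, alternate contacts at facility | 11% to 33% | 100% |
| 4+ visits, all eight at facility | 44% to 83% | 100% |
| Mean contacts | 3.1 to 5.5 | 8 |
| Mean weighings, four evenly spaced | 1.6 to 2.7 | 4 |
| Mean weighings, alternate contacts | 1.8 to 3.0 | 4 |

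The counts are thus cut to roughly 40% to 75% of their full value (3.1/8 = 39%; 3.0/4 = 75%).

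**Effect on an arm difference.** As an illustration, let one arm receive 8 evenly spaced contacts and the other 4, over the same weeks. The true difference is 4. In PW it would appear as 3.11 − 1.56 = 1.6 at the low end and 5.50 − 2.67 = 2.8 at the high end.

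**Effect of gestational-age mix.** Spacing is (l − f)/7, from 24/7 = 3.4 to 32/7 = 4.6 weeks. For women within the schedule, a two-week arm difference in gestational age moves the count by 2/4.6 = 0.4 to 2/3.4 = 0.6 contacts with no difference in delivery.

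**If the samples were pooled at planned sizes.** Perfect delivery would show (960 + 480 × 0)/1,440 = 67% to (960 + 480 × 0.167)/1,440 = 72% with 8+ contacts, instead of 100%.

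**The case against.** Much can be said for the plan. The threshold rows carry an RDW label, so it is not settled that they will be computed in PW. RDW remain a source on every disputed row, so whole-pregnancy values will be available. SAP section 3.3 assigns every formal impact estimate other than dietary diversity to RDW. Truncation acts in both arms. Section 3.2 reports trimester by arm at both surveys, so a marked imbalance would be visible. Delivery is also traced through provider training, knowledge and service provision.

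All of this stands, and it limits the point to a supportive analysis. It does not remove it: the four unlabelled counts would be computed in PW under the source column, and reporting trimester does not adjust the pathway comparison.

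A reader might infer more, in three ways that the documents do not support:

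- That all these indicators sit near the floor in PW. Only 8+ contacts does so under every schedule tried. The result for 4+ visits depends on the schedule, and weighings are a shortened count.
- That the pathway reading would be reversed. A cut-off common to both arms shrinks a difference; nothing shows a change of sign.
- That the programme's early identification of pregnant women (Protocol Table 1) would bring earlier pregnancies into the intervention arm's sample. PW are drawn at random from a village census (Protocol 2.6), and earlier entry to care would also raise the count at a given gestation, which works the other way.

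**Conclusion.** The point holds as a conflict between label and source column in Table 7, together with an unadjusted count-to-date in PW. Its consequences are attenuation, added noise and dependence on the gestational-age mix by arm and survey round. They fall on the PW side of the plausibility analysis. Both primary outcomes and all RDW-based estimates are untouched.

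The sizes rest on a uniform gestational age, even spacing and full attendance, none of which the documents state. The direction needs only that PW are interviewed before their pregnancies end.

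**What to change.** In Table 7, take the completed-pregnancy indicators (4 or more visits, 8 or more contacts, weighed 4 or more times, and whole-pregnancy totals) from RDW only, as Table 3 already does.

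For the PW pathway to dietary diversity, define exposure-to-date indicators: any antenatal contact so far, any counselling on dietary diversity so far, and number of contacts so far. The existing alternative of being weighed at each visit attended also suits PW, because it does not need a finished pregnancy. Label these rows as PW, report them separately from RDW in Table 8, and add gestational age at interview as a covariate in the section 3.4.2 models.

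The cost is SAP wording. Gestational age is already recorded in module 3 of the PW questionnaire, and antenatal use and community exposure in modules 4 and 5 (Protocol Table 8), so no new data are needed.
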